4.2 Study Patients

4.2.1 Disposition of Patients

The following information will be tabulated:

- Number of patients screened, number of patients included in each analysis set, and reasons for exclusion from analysis sets
- Completion of treatment phase, reason for premature discontinuation
- Treatment duration: Duration of trial product administration during treatment phase [days]

Duration of trial product administration will be calculated as date of last administration – date of first administration +1.

• Study duration: Last visit during treatment phase

Last visit during treatment phase will be the last visit of V1 to V12 where a visit date is documented in the eCRF.

• Study duration: Follow-up visit performed

This will be 'yes', if a visit date is documented at the follow-up visit and 'no' otherwise.

4.2.2 Protocol Deviations

The following protocol deviations will be tabulated:

- Violation of inclusion/exclusion criteria
- Compliance with time window for Week 52 (EOT): Difference between date of baseline visit date and date of Week 52 (EOT) within or outside the allowed window, for patients who completed the treatment phase.

4.2.3 Demographic and Other Baseline Characteristics

The following demographic data, SBS characteristics and history, medical history/concomitant illness and other baseline data will be summarized using descriptive statistics. Other baseline characteristics data will be listed.

- Demographic data:
 - o Sex,
 - o Age [years] (calculated as date of baseline visit minus date of birth divided by 365),
 - o Race,
 - o Ethnicity
- SBS characteristics and history:
 - o Type of SBS
 - Severity of SBS based on the ESPEN Functional and Clinical Classification of Chronic Intestinal Failure
 - Cause of SBS
 - o Time since diagnosis of underlying disease
 - Time since SBS diagnosis
 - o Surgery:
 - Time since most recent resection
 - Reason for resection
 - Remaining bowel sections:
 - Colon-in-continuity (including type)
 - End-jejunostomy/SBS anatomical group 1
 - Ileostomy/SBS anatomical group 1
 - Colostomy
 - Presence of ileocecal valve
 - o Bowel lengths
 - Length of the remnant small bowel
 - The remnant colon in percent (according to Cummings classification)
 - o Time since start of PS, if applicable.

Time since diagnosis of underlying disease [months] will be calculated as follows: (date of baseline visit – date of diagnosis of underlying disease) [number of days]/30.5.

Time since SBS diagnosis [months], time since most recent resection [months] and time since start of PS [months] will be calculated analogously.

In case of an incomplete date of diagnosis of underlying disease, date of SBS diagnosis, date of most recent resection or date of start of PS (if applicable), a missing day will be replaced with "15" and a missing month will be replaced with "July" for the calculation. Negative time, which may occur rarely because of the replacement of missing days or months, will be set to missing.

- Medical History/Concomitant Illness
 - Encephalopathy
 - o Ascites
 - Cholestasis
 - Steatosis
 - Cirrhosis
- Substance Abuse:
 - Alcohol abuse
 - o Drug abuse
 - Tobacco smoking
- Body weight (kg) at baseline and body height (cm) at screening (may be included in the tabulation of demographic data).

4.2.4 Drug Exposure and Treatment Compliance

The selected dose for this trial is 10 mg glepaglutide once-weekly for 52 weeks. Summary tables presenting descriptive statistics will be provided for:

- Drug exposure
- Treatment compliance.

Drug exposure will be measured by the number of trial product administrations per patient.

Treatment compliance will be calculated by dividing the actual number of trial product administrations per patient by the number of trial product administrations theoretically to be applied during the patient's individual treatment period. That means, the actual number of trial product administrations per patient will be divided by [1 + the number of weeks until visit Week 52 (EOT)], whereby number of weeks is the integer part of {[date of Week 52 (EOT) visit – date of first administration of trial product] / 7}. The result will be multiplied by 100 to obtain a percentage.

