#### 4.3 Justification for Dose

The selected dose for this trial is 10 mg glepaglutide once-weekly for 52 weeks. The selected dose is considered supported with respect to both safety and efficacy, as described below.

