### 6.8 Treatment After the End of the Trial

When discontinuing trial product (Visit 12), the patient should be treated according to the standard of care at the discretion of the Investigator or treating physician.

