### • PROs:

- Ocopies of PGIC, SBS-I and EQ-5D-5L questionnaires can be sent to the patients for completion, including the standard instructions for how to complete, date, and sign. The instructions include among other things the following notes; It is important the SBS-I is completed by the patient without assistance of family members.
- o Patients should:
  - Fill in the PROs and complete the questionnaires on the same day as the remote visit is scheduled, but prior to the site visit call.
  - Send a copy of completed PROs to site for review and entry into eCRF.
  - Bring original documents to site at next possible visit. These documents will be source data to be verified at that point. If source data is lost, then copies received will suffice.
- Trial product can be sent directly from the site to the patient's home
- Visit 9 can be postponed, until on-site visit is possible again. After 24 weeks of treatment, the patient will be in a stable treatment, and postponing the visits is not expected to affect the assessments
- The EoT visit can be postponed (time window can be extended up to + 8 weeks)

Deviations from the protocol caused by circumstances related to the pandemic will be documented. Handling of data affected by the pandemic situation will, if applicable, be addressed in the statistical analysis plan.

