3.2 Per-protocol Set

The PPS comprises all FAS patients without major protocol deviations.

Major protocol deviations may include:

- Violation of one or more relevant inclusion/exclusion criteria
- Absence of on-treatment data
- Insufficient compliance with administration of trial product
- Use of prohibited concomitant therapy
- Insufficient compliance with other procedures/instructions like
 - Deviation from fixed drinking menu / PS volume / Urine volume collection
 - Deviation concerning collection of urine/feces:

An answer of "No" to one or more of the following questions in the eCRF

- Fasting requirement (PS allowed) (Day 2)
- Urinate / defecate / empty stoma bag prior to MBS collection start (Day 2)
- Collection of duplicate food and liquids (Day 2/3/4)
- Urinate / defecate / empty stoma bag end of study (Day 4)
- Other relevant protocol deviations.

The final allocation to and exclusion from the PPS will be made prior to database lock and will be approved by the sponsor. The PPS will be used for supplementary analyses of the primary and key secondary efficacy endpoints.

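### The SAP compliance formula counts one unscheduled dose when the EOT visit falls on a weekly dosing day, and keeps counting doses for patients who stop drug but stay in the trial

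*SAP*

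**What the plan says.** SAP 4.2.4 defines compliance as administrations taken divided by "the number of trial product administrations theoretically to be applied during the" patient's own treatment period. It then makes this operational as "1 + the number of weeks until visit Week 52 (EOT" visit), where "number of weeks is the integer part of" the days from first dose to that visit divided by 7.

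On the regimen, Protocol 4.3 states: "The selected dose for this trial is 10 mg glepaglutide once-weekly for 52 weeks". No dose count is given. Protocol 6.8 opens with "When discontinuing trial product (Visit 12"), so drug stops at that visit. The administration row of the Protocol 1.2 flowchart marks only Visits 1 and 9, and no product is dispensed at Visit 12. Visit 12 has a window of ±14 days; under the COVID-19 provisions in Protocol 8.1.7 the "time window can be extended up to + 8 weeks".

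Protocol 7.1 wants patients who stop drug to remain in the trial on the planned visit schedule. SAP 2.1.1.1 holds the EOT examination at withdrawal for patients who leave the trial. SAP 5 repeats the formula up to the Visit 9 cut-off and substitutes the withdrawal date for patients withdrawn earlier. SAP 3.2 lists "Insufficient compliance with administration of trial product" among possible major deviations, with no percentage threshold.

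**The concern.** The formula does not match its own description in two ways. First, adding 1 to the whole weeks counts every dosing day from first dose through the EOT visit day inclusive, while the protocol schedules no dose on that day. Second, the end of the count is the EOT visit, not the end of treatment. Two patients with identical exposure can therefore get very different scores, depending only on whether they stayed for follow-up.

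At stake are the reported compliance table (Table 1-4) and any per-protocol exclusion that leans on the percentage. Protocol 9.2 plans to enroll 10 patients, so one misjudged exclusion would remove about a tenth of the set.

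**Working it through.** The documents state no compliance percentage, dose count or threshold, so there is no figure to reproduce. The formula was evaluated directly.

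**Set-up.** Let d be the days from first dose to the EOT visit. Doses fall due on days 0, 7, 14 and so on.
- SAP denominator: 1 + floor(d/7).
- Doses due before the EOT day: ceiling(d/7).
- The two differ by 1 when d is a multiple of 7 and agree otherwise.

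**Nominal Week 52, d = 364.** The SAP denominator is 1 + 52 = 53. Doses due before the visit are 364/7 = 52, on days 0 to 357. Full compliance scores 52/53 = 98.11%.

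**Other EOT dates.** The documents do not say whether weekly dosing continues to a delayed visit, so a fully compliant patient is scored both ways:

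| d | SAP denominator | Dosing ends at 52 doses | Dosing continues to the day before EOT |
|---|---|---|---|
| 350 | 51 | 50/51 = 98.0% | 50/51 = 98.0% |
| 351–356 | 51 | 51/51 = 100% | 51/51 = 100% |
| 357 | 52 | 51/52 = 98.1% | 51/52 = 98.1% |
| 358–363 | 52 | 52/52 = 100% | 52/52 = 100% |
| 364 | 53 | 52/53 = 98.1% | 52/53 = 98.1% |
| 365–370 | 53 | 52/53 = 98.1% | 53/53 = 100% |
| 371 | 54 | 52/54 = 96.3% | 53/54 = 98.1% |
| 372–377 | 54 | 52/54 = 96.3% | 54/54 = 100% |
| 378 | 55 | 52/55 = 94.5% | 54/55 = 98.2% |
| 420 (+8 weeks) | 61 | 52/61 = 85.2% | 60/61 = 98.4% |

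Of the 29 days in the ±14-day window, full compliance scores 100% on 24 if dosing continues to the visit and on 12 if it ends at 52 doses.

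**Stopping drug but staying in the trial.** After 24 doses the last dose is on day 23 × 7 = 161.
- EOT visit at day 364: 24/53 = 45.3%.
- EOT visit at days 162 to 167: denominator 1 + 23 = 24, so 24/24 = 100%.
- EOT visit at day 168: 24/25 = 96.0%.

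With an EOT visit at day 364, 12 doses score 12/53 = 22.6% and 40 doses score 40/53 = 75.5%.

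**Interim count.** Visit 9 dosing follows the treatment schedule, so a dose can fall on the cut-off day. At day 168 that dose is the 25th, and the SAP formula gives 25/(1 + 24) = 100%. An exclusive count would give 25/24 = 104.2%. The run-on remains, however: 12 doses followed by continued attendance to day 168 score 12/25 = 48.0%.

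**The case against.** For doses on days 0, 7, 14 and so on, 1 + floor(d/7) is the correct count through day d; it over-counts only when the EOT visit lands on a dosing day. That stands. A reader might infer that full compliance always scores 98% or less, or that reported compliance is systematically too low. The documents do not support this. The denominator ranges from 51 to 55 within the window, the nominal score is slightly above 98%, and many visit dates give 100%. If a site counts Week 52 from admission, three days before first dose, d = 361 and the score is 52/52 = 100%.

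The lowest figures in the table, 94.5% and 85.2%, are also tempting to cite. They assume that a patient stops at 52 doses and waits off drug for a late visit, which no passage states; the second also needs the COVID-19 extension.

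On the run-on, a low score for someone who stops early can be defended as adherence to the full planned regimen. But that is not how SAP 4.2.4 describes its denominator, and the formula does not apply it to patients who leave the trial. SAP 4.3.1 does say that collection of treatment-phase data ends on withdrawal from the treatment phase. If an EOT visit were held then, the run-on would not arise, but Protocol 7.1 keeps such patients on the planned schedule.

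It also stands that the consequence is small. SAP 3.2 sets no threshold and does not cite the 4.2.4 percentage, the per-protocol analysis is supportive, and the FAS analysis uses data regardless of compliance.

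**Conclusion.** The point holds as a limited formula error with two parts. When the EOT visit falls on a dosing day, one unscheduled dose is counted, costing about 2 percentage points (98.1% at day 364). For patients who stop drug but stay in the trial, the denominator runs past the end of treatment, and this effect can be large: 45% against 100% for the same 24 doses. The first part assumes doses on exact weekly days from first dose and none on the EOT day. The second assumes that patients who stop drug keep the planned schedule, as Protocol 7.1 intends. No FAS primary or key secondary result changes.

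**What to change.** **Final analysis (SAP 4.2.4).** Define the denominator as the weekly doses due from first dose up to, but not including, the earlier of the EOT visit date and the date of permanent treatment discontinuation, that is ceiling(days/7). At day 364 this gives 52/52 = 100%. For 24 doses with discontinuation dated on days 162 to 168 it gives 24/24 = 100%.

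State that the discontinuation date is the date of the decision to stop, or count numerator and denominator over the same interval. If the last-dose date (day 161) were used with an exclusive count, the score would be 24/23 = 104.3%.

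Do not cap at 52: if dosing continued to an EOT visit 14 days late, a cap would give 54/52 = 103.8%.

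**Interim analysis (SAP 5).** Keep the existing count through the Visit 9 cut-off date, because a dose may be given during that visit. End it at permanent treatment discontinuation as well as at withdrawal.

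**Delayed Visit 12.** The 52-week regimen and the delayed-visit provisions must be reconciled on whether weekly dosing continues to a late visit; the compliance count should then follow that answer.

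Early stopping needs no new table, since SAP 4.2.1 already tabulates premature discontinuation and treatment duration. The cost is a short change to SAP wording and the matching program, using dates already planned for collection.

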4.2.5 Pre-treatment and Concomitant Therapy

Pre-treatment therapies are defined as treatments with stop date prior to date of first dose (including those with incomplete start date). Concomitant therapies are subdivided into 1) treatments ongoing or commenced at the date of first dose and 2) treatments commenced after the date of first dose. Depending on the start date, therapies with incomplete stop date are allocated to concomitant therapy group 1) or 2). All other therapies (therapies with unknown start and/or stop date which can not be allocated to one of the categories above) will be allocated to all three therapy groups.

Pre-treatment and concomitant therapies will be coded and frequencies will be calculated by the first and the fourth level of the Anatomical Therapeutical Chemical (ATC) classification. Separate summary tables will be provided for pre-treatment, concomitant therapies ongoing or commenced at the date of first dose and concomitant therapies commenced after the date of first dose.

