### Medical history and concomitant diseases

- 5. More than 2 SBS-related or PS-related hospitalizations (e.g., catheter-related bacteremia/sepsis, bowel obstruction, severe water-electrolytes disturbances, etc.) within 6 months prior to screening.
- 6. Poorly controlled inflammatory bowel disease (IBD) that is moderately or severely active or fistula interfering with measurements or examinations required in the trial.
- 7. Current bowel obstruction.
- 8. Known radiation enteritis or significant villous atrophy, e.g., due to active celiac disease.
- 9. Cardiac disease defined as: decompensated heart failure (New York Heart Association [NYHA] Class III-IV), unstable angina pectoris, and/or myocardial infarction within the last 6 months prior to screening.
- 10. Clinically significant abnormal electrocardiogram (ECG) as judged by the Investigator.
- 11. Human immunodeficiency virus (HIV) positive, acute liver disease including positive results for Hepatitis B antigens (HBsAg) and Hepatitis C (HCV), or unstable chronic liver disease.
- 12. Any history of colon cancer. History of any other cancers (except margin-free resected cutaneous basal or squamous cell carcinoma or adequately treated in situ cervical cancer) unless disease-free state for at least 5 years.
- 13. Hepatic impairment defined as:
  - a. Total bilirubin  $\geq 2 \times$  the upper limit of normal (ULN), or
  - b. Aspartate aminotransferase (AST)  $\geq$  5 × ULN, or
  - c. Alanine aminotransferase (ALT)  $\geq$  5× ULN
- 14. Use of GLP-1, GLP-2, human growth hormone (HGH), somatostatin, or analogs thereof, within 3 months prior to screening.
- 15. Known or suspected hypersensitivity to glepaglutide, its components or related products.
- 16. Use of dipeptidyl peptidase (DPP)-4 inhibitors within 3 months prior to screening.
- 17. Surgical resection of gut tissue within 6 months prior to screening.
- 18. Systemic immunosuppressive therapy for treatment of the gastrointestinal tract that has been introduced or has been unstable within 3 months prior to screening.
- 19. Unstable biological therapy (e.g. anti-TNF-α, natalizumab, etc.) within 6 months prior to screening, including significant changes in doses or switch of drug.

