#### 6.6 Prohibited Medication

GLP-1 analogs, GLP-2 analogs (teduglutide), HGH, DPP-4 inhibitors, and somatostatins are not allowed to be used by patients during the course of the trial.

Medications commonly used to treat SBS symptoms including anti-diarrhea agents are allowed during trial participation; however, changes (start, stop, new brands, or dose changes) should be kept to a minimum and the reason for the change should be recorded in in eCRF. Any changes to concomitant medications must be documented in the eCRF.

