### 8.1.5 Concomitant Medication

All prescription and non-prescription medications taken within 7 days prior to and including the screening visit will be recorded in the eCRF. Any changes to concomitant medications that occur throughout the trial will be recorded (see Section 6.5).

All relevant previous treatments, including treatment with teduglutide, any other GLP-2 analogs or native GLP-2 are recorded in the eCRF.

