1-6.2	Protocol deviations	ENR	Type of deviation with specification and details; minor or major; reason if minor
1-7	Trial product administration	ENR	Diary Trial Drug Administration form
1-8	Treatment compliance	ENR	All related variables
1-9.1	Demographic data (Part 1)	ENR	Sex, age, race, ethnicity; height, weight; BMI (Demographics and Body Measurements forms)
1-9.2	Demographic data (Part 2)I: Women related information	ENR	Child-bearing potential; Pregnancy Test (Demographics and Pregnancy Test forms)
1-10.1	SBS characteristics and history (Part 1)	ENR	Type, severity and cause of SBS; Time since diagnosis of SBS and of underlying disease; Use of PS at Screening (SBS characteristics and history form)
1-10.2	SBS characteristics and history (Part 2)	ENR	Surgery (including time since most recent resection), remaining bowel sections and bowel lengths (SBS characteristics and history form)
1-11	Medical History/Concomitant Illness	ENR	Any medical condition or event; Medical condition or event; start date; Ongoing at screening; End date; Relatedness to SBS; MedDRA coding (Medical History/Concomitant Illness Header and cont. forms)
1-12	Medical history - SBS	ENR	Encephalopathy, ascites, cholestasis, steatosis and cirrhosis related variables (Medical History – SBS form)
1-13	Substance Abuse	ENR	Substance Abuse form
1-14	Colonoscopy	ENR	Colonoscopy form
1-15	HIV, Hepatitis B and C	ENR	HIV, Hepatitis B and C form
1-16	Drinking Menu	ENR	Drinking Menu and Set Drinking Menu forms

No.	Title	Set	Variables to be included/Variables of the following form in the eCRF and corresponding derived variables
1-17	Physical examination at screening	ENR	Performed; Date; Systems assessed; Evaluation; Clinical Significance (Physical Examination form)
1-18	Parenteral Support Prescription	ENR	Parenteral Support Prescription form
1-19.1	Concomitant medication (Part 1)	ENR	ATC Levels including preferred name and code
1-19.2	Concomitant medication (Part 2)	ENR	CM Number; Indication; Dose (Concomitant Medication form)
1-19.3	Concomitant medication (Part 3)	ENR	Route of Administration; Specification other route of administration; Start and End of drug therapy; Therapy ongoing; Used pre- treatment;(Concomitant Medication Form); Concomitant medicationcategory (pre-treatment, at first dose, after first dose)
1-20	Formal fields (several parts)	ENR	

No.	Title	Set	Variables				
Efficacy	Efficacy Evaluation and Other Variables						

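### SAP 4.2.5 counts a past therapy with an incomplete stop date as ongoing at first dose, even when the known year or month shows that it ended earlier

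*SAP*

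**What the plan says.** SAP 4.2.5 uses three groups.

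- Pre-treatment: "Pre-treatment therapies are defined as treatments with stop date prior to date of first dose (including those with incomplete start date".
- Concomitant, in two parts: "1) treatments ongoing or commenced at the date of first dose and 2) treatments commenced after the date of first dose".
- Partial stop dates: "Depending on the start date, therapies with incomplete stop date are allocated to concomitant therapy group 1) or 2".
- Everything left over, described as "therapies with unknown start and/or stop date which can not be allocated to one of the categories above", goes into all three groups.

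The groups feed Tables 1-5.1 (pre-treatment), 1-5.2 (group 1) and 1-5.3 (group 2), as frequencies at ATC levels 1 and 4. SAP 4.5 replaces no missing values unless stated, and nothing is stated for therapy dates. Listing 1-19.3 in SAP Appendix B shows "Start and End of drug therapy; Therapy ongoing", an item for use before treatment, and the derived category.

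The protocol makes old therapy records foreseeable. Section 8.1.5 says: "All relevant previous treatments, including treatment with teduglutide, any other GLP-2 analogs or native GLP-2 are recorded in the eCRF". Exclusion criterion 14 in Section 5.2 covers only recent use: "Use of GLP-1, GLP-2, human growth hormone (HGH), somatostatin, or analogs thereof, within 3 months prior to screening". A patient who stopped earlier than that can enter. During the trial the class is barred (Section 6.6): "GLP-1 analogs, GLP-2 analogs (teduglutide), HGH, DPP-4 inhibitors, and somatostatins are not allowed to be used by patients during the course of the trial".

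**The concern.** The pre-treatment definition tolerates an incomplete start date but not an incomplete stop date. A therapy whose stop day or month was not recorded therefore cannot be classed as pre-treatment alone, however clearly the known year shows that it had ended. The rule discards information that the eCRF holds.

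This is a single-arm trial, so the therapy tables are one of the places where a reader checks what else patients were taking around first dose. Protocol 6.5 asks for changes in SBS medication to be kept to a minimum. A past course counted as ongoing at first dose, or as started after it, gives that reader a wrong count. The records at risk include past courses of the trial drug's own class, which the protocol asks sites to record and sets no look-back limit for.

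**Working it through.** The plan gives no figure to reproduce, so the check applies the sentences of SAP 4.2.5 literally to example records.

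**Assumption.** First dose on 1 October 2021. The synopsis estimates the first visit for Q3 2021, and any date in the planned trial period gives the same results.

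**Rule as written**

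1. Complete stop date before first dose: pre-treatment.
2. Stop date incomplete or unknown, start on or before first dose: group 1.
3. Stop date incomplete or unknown, start after first dose: group 2.
4. Stop date incomplete or unknown, start cannot be placed: all three groups.

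**Comparison rule.** Take the latest date compatible with the known parts of the stop date. For 2018 alone this is 31 December 2018; for May 2016 it is 31 May 2016; for 2016 alone it is 31 December 2016. If that date is before first dose, the therapy is pre-treatment only. Otherwise the rule as written applies.

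| Start | Stop | SAP 4.2.5 as written | Comparison rule |
|---|---|---|---|
| 10 Mar 2014 | 2 May 2016 | pre-treatment | pre-treatment |
| 10 Mar 2014 | May 2016 | group 1 | pre-treatment |
| 10 Mar 2014 | 2016 | group 1 | pre-treatment |
| 1 Mar 2016 | 2018 | group 1 | pre-treatment |
| 2016 | 2018 | group 1 | pre-treatment |
| unknown | 2016 | all three | pre-treatment |
| unknown | 2 May 2016 | pre-treatment | pre-treatment |
| 2014 | unknown | group 1 | group 1 |
| unknown | unknown | all three | all three |

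Rows 1 and 2 isolate the cause: dropping the stop day alone moves a course that ended more than five years earlier from pre-treatment to ongoing at first dose. Rows 3 to 6 are also misplaced, although the known year settles them.

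**The opposite error.** A drug marked ongoing has no stop date. If its start is unknown, step 4 puts it into all three groups. One of these is pre-treatment, which the SAP defines by a stop before first dose. An ongoing drug cannot meet that definition.

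**Size.** Protocol 9.2 plans to treat 10 patients; the synopsis allows up to 16.

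- One affected patient in 10: 1/10 = 10%.
- One in 16: 1/16 = 6.25%.
- SAP 4.1 also tabulates SBS-IF and SBS-II separately. With the intended equal split of 10 patients, each column has 10/2 = 5, so one patient is 1/5 = 20%.

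How many such records exist cannot be known from the documents.

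**The case against.** The best defence is that SAP 4.2.5 can be read coherently. A stop in 2018 is before first dose, so the course meets the pre-treatment definition, and the later sentence covers only incomplete stop dates that leave the question open. That may be the intent. But the later sentence contains no such limit, and the definition's stated allowance is for the start date only. On this reading two sentences still send one record to different tables, so two programmers could produce different counts.

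A second defence is that over-inclusion is a deliberate worst-case choice, as in SAP 4.4, where an adverse event with an incomplete start date is treated as treatment-emergent. That is sound when the known parts leave the timing open. It gives no reason to override a year that settles it. SAP 4.2.3 keeps the known parts of partial dates for diagnosis, resection and start of parenteral support.

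Several stronger inferences are tempting, and the documents do not support them.

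- *That a course from 2016 to 2018, years only, enters all three groups.* It does not. The start year is incomplete but not unknown, and it lies wholly before first dose, so the record goes to group 1 only.
- *That the tables would name a prohibited GLP-2 analog.* They report ATC levels 1 and 4. The preferred name is specified for Listing 1-19.1, and Listing 1-19.3 prints the dates and status items beside the category.
- *That a false breach of eligibility or a per-protocol exclusion would follow.* Eligibility has its own outputs (Tables 1-2.1 and 1-2.2, Listing 1-2) and deviations have a log (Listing 1-6.1). Per-protocol allocation is settled before database lock with sponsor approval (SAP 3.2). None is stated to use these categories; a misplaced record could at most mislead someone reviewing them.
- *That the tables become useless for judging stable SBS medication.* A drug with a placeable start is never falsely shown as started after first dose. Only records whose start cannot be placed are spread.

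Two limits also stand. Protocol 8.1.5 does not say which form holds earlier GLP-2 treatment, so its entry into Tables 1-5.1 to 1-5.3 is an assumption. Other medication is collected only from 7 days before screening, so old stop dates should be uncommon outside that history.

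**Conclusion.** The point holds as a minor, descriptive error in a stated rule. Read as written, SAP 4.2.5 counts a past therapy with a partial stop date as ongoing at first dose even when the known parts show that it had ended. When the start cannot be placed either, the record is also counted as started after first dose. A drug marked ongoing with an unplaceable start is also counted as pre-treatment, against the SAP's own definition.

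The reach is Tables 1-5.1 to 1-5.3 and the derived category in Listing 1-19.3. The primary and key secondary analyses use the full analysis set with a treatment policy strategy and do not depend on therapy categories. The percentages above are per affected patient, and rest on at least one such record reaching these tables.

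**What to change.** Replace the incomplete-stop-date and residual sentences of SAP 4.2.5 with rules to this effect:

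1. Assign a therapy to pre-treatment alone if the latest date compatible with the known parts of its stop date is before first dose. Where the date parts leave this open, do the same if the eCRF marks it as used before treatment and not ongoing.
2. Never assign a therapy marked ongoing to pre-treatment.
3. Keep multi-group allocation only where the known date parts and the eCRF items cannot place the record relative to first dose, and flag those records in Listing 1-19.3.

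The documents do not define the two eCRF items. Before programming, confirm against the eCRF instructions that used before treatment and not ongoing means that use ended before first dose.

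The cost is a few SAP sentences and a few lines of code. Both items are already collected, so no new data are needed.
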